minimum of two years after the last approval of the marketing application, or at least five years after formal discontinuation of clinical development of the investigational product. These documents should be retained for a longer period, however, if required by the applicable regulatory requirements or by an agreement with the Sponsor.

If the investigator retires, relocates, or for other reasons withdraws from the responsibility of keeping the study records, custody must be transferred to a person who will accept responsibility.

Publication policy

The Sponsor and Investigators are committed to the publication and widespread dissemination of the results of the study. This study represents a joint effort between the Sponsor and Investigators, and as such, the parties agree that the recommendation of any party concerning manuscripts or text shall be taken into consideration in the preparation of final scientific documents for publication or presentation. All proposed publications and presentations by Sponsor and Investigators or their personnel and associates resulting from or relating to the study must be submitted to the Steering Committee for review and approval before submission for publication or presentation. If any such proposed publication or presentation contains patentable subject matter which in Sponsor's sole discretion, warrants intellectual proprietary protection, Sponsor may delay any publication or presentation for up to thirty (30) days after Steering Committee approval to pursue such protection.

REFERENCES

APPENDIX I - DEFINITIONS AND ACRONYMS

Acute gain: post-procedure minimal lumen diameter (MLD) minus the pre-procedure MLD measured by Quantitative Coronary Angiography (QCA).

ADE (Adverse Device Effect): Adverse effects on health or safety or any life-threatening problem or death caused by or associated with a device, if that effect, problem, or death was not previously identified in nature, severity or degree of incidence in the investigational plan or IDE application, or any other unanticipated serious problem associated with a device that relates to the rights, safety, or welfare of patients.

AE (Adverse Event): Any undesirable clinical event occurring to a subject, during a clinical Registry, whether or not considered related to the investigational product(s).

Angiographic Thrombosis/Occlusion: Angiographic thrombosis is defined as the angiographic documentation of either a complete occlusion (TIMI flow 0 or 1) or an angiographic documentation of a flow limiting thrombus (TIMI flow 1 or 2). A Subacute Occlusion is defined as occurring after removal of the guiding catheter, before 30 days follow-up.

ASA: Acetylsalicylic acid: Chemical name for aspirin; a drug having antiplatelet, anti-inflammatory, analgesic, and antipyretic effects.

Bleeding complications: Bleeding will be considered major if:

1. it leads to death;
2. it leads to permanent disability;
3. it is clinically suspected or proven to be intracranial (see stroke)
4. it produces a fall in hemoglobin of at least 3 mmol/l;
5. it leads to transfusion of 2 or more units of whole blood of packed cells;
6. Peripheral vascular surgery is necessary.

All other bleeding will be considered as minor.

Braunwald classification of unstable angina

Severity

Class 1: New onset of severe or accelerated angina. Patients with new onset (<2 months in duration) exertional angina pectoris that is severe or frequent (<3 episodes/day) or patients with chronic stable angina who develop accelerated angina (that is, angina distinctly more frequent, severe, longer in duration, or precipitated by distinctly less exertion than previously) but who have not experienced pain at rest during the preceding 2 months.

Class 2: Angina at rest, subacute. Patients with one or more episodes of angina at rest during the preceding month but not within the preceding 48 hours.

Class 3: Angina at rest, acute. Pts with one or more episodes of angina at rest within the preceding 48 hours.

Clinical circumstances in which unstable angina occurs:

Class A: Secondary unstable angina. Patients in whom unstable angina develops secondary to a clearly identified condition extrinsic to the coronary vascular bed that has intensified myocardial ischemia. Such conditions reduce myocardial oxygen supply or increase myocardial oxygen demand and include anemia, fever, infection, hypotension, uncontrolled hypertension, tachyarrhythmia, unusual emotional stress, thyrotoxicosis, and hypoxemia secondary to respiratory failure.

Class B: Primary unstable angina. Patients who develop unstable angina pectoris in the absence of an extra cardiac condition that have intensified ischemia, as in class A.

Class C: Post infarction unstable angina. Patients who develop unstable angina within the first 2 weeks after a documented acute myocardial infarction

CABG: Coronary Artery Bypass Graft.

CCS (Canadian Cardiovascular Society) classification

Class I: Ordinary physical activity, such as walking and climbing stairs, does not cause angina. Angina with strenuous, rapid, or prolonged exertion at work or recreation.

Class II: Slight limitation of ordinary activity. Walking or climbing stairs rapidly, walking up hill, walking or stair climbing after meals, in cold, in wind, or when under emotional stress or during the first few hours after awakening may cause pain. Walking more than two blocks on the level and climbing more than one flight of stairs at a normal pace and in normal conditions.

Class III: Marked limitation of ordinary physical activity. Walking one-two blocks on a level and climbing one flight of stairs at normal pace results in angina.

Class IV: Inability to carry on any physical activity without discomfort. Anginal syndrome may be present at rest.

De novo lesion: A coronary lesion not previously treated.

Dissection NHLBI classification National Heart Lung and Blood Institute:

A – Intraluminal radiolucent defect

B – Extraluminal “cap” (without staining)

C – Extraluminal “cap” with persistence of dye (staining)

D – Spiral defects

E – Persistent filling defect

F – Filling defect with total occlusion

Note: Types E & F dissections may be caused by thrombus

DS (Diameter Stenosis):

Percent DS – Value calculated as $100 * (1 - (MLD/RVD))$. A 100 %DS is imputed for total occlusions.

Late loss:

Late lumen loss is defined as the difference in minimal lumen diameter (MLD) between post-procedural and follow-up in mm

MACE (Major Adverse Cardiac Events):

Composite of Death (Both Cardiac & Non-Cardiac Death), MI (Q-wave and Non-Q-wave), (emergent)

CABG or clinically driven Target Lesion Revascularization (TLR).

Major vascular complications:

All pseudoaneurysms, vascular access site bleeding associated with a decrease in hemoglobin ≥ 3.0 mmol/L as well as vascular events which required surgical repair or transfusion of > 2 units within 30 days of the procedure.

MI (Myocardial Infarction):

Necrosis of the myocardium, as a result of interruption of the blood supply to the area, as in coronary thrombosis.

MI, non-Q-Wave:

Elevation of post-procedure CK levels to > 2 times normal with elevated CK-MB in the absence of pathological Q waves. If no assay for CK-MB was performed, elevation of CK levels to > 2 times normal without new Q waves is also considered a non-Q-wave MI.

MI, Q-Wave:

MI, Q-Wave Development of new, pathological Q waves in 2 or more contiguous leads (as assessed by the investigator and confirmed by the Clinical Endpoint Committee) with post-procedure CK-MB levels elevated above normal.

MLD (Minimal Lumen Diameter):

MLD (Minimal Lumen Diameter) Mean Minimal Lumen Diameter (mm).

Procedure success rate: Percentage of patients with angiographic success and without the occurrence of MACE during the index hospitalization.

QCA (Quantitative Coronary Angiography, off-line):

Off-line refers to assessment at the Angiographic Core Laboratory. The method is a quantitative estimate obtained with a digital angiographic computer utilizing an automatic edge detection algorithm.

RVD (Reference Vessel Diameter):

Interpolated reference diameter.

SAE (Serious Adverse Event):

An adverse event is defined as serious, whenever the adverse event is fatal, life-threatening, results in persistent or significant disability/incapacity, requires inpatient hospitalization or prolongation of hospitalization, results in fetal death or distress, is a congenital anomaly/birth defect and in cases of cancer/malignancy.

Stroke:

A focal neurological deficit, resulting from a vascular cause involving the CNS, of sudden onset that is not reversible within 24 hours (including death) and which is not due to a readily identifiable cause (i.e. brain tumor, trauma).

TLR (Target Lesion Revascularization):

Any repeat treatment of the stented segment including 5 mm proximal and 5 mm distal from the edge of the stent.

TVF (Target Vessel Failure):

Cardiac Death, MI (Q-wave and non-Q-wave) or Target Vessel Revascularization (TVR) that could not be clearly attributed to a vessel other than the target vessel.

TVR (Target Vessel Revascularization):

Revascularization of any segment of the index coronary artery, which was in physical contact with any component (guiding catheter, guidewire, balloon catheter, etc.) of the angioplasty hardware during the initial procedure

TWS (Technician's Work Sheet):

Part of the CRF used to specify the details of the angiographic procedure and the angiographic observations.

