Secondary Objectives:

Device success, procedural success, angioplasty outcomes, MACE at 6/12 months, TLR at 6/12 months, SAEs, MACE-free survival.

Endpoints:

Primary Endpoint:

MACE at 30 days.

Secondary Endpoints:

Device success, procedural success, post-usage angioplasty results, MACE at 6/12 months, TLR, TVR, SAEs, MACE-free survival.

Study Population:

Sample Size: 360 subjects

Inclusion/Exclusion criteria:

Inclusion Criteria:

Those subjects eligible for and who met the following inclusion/exclusion criteria were enrolled in this study.

1. Adults ≥ 18 yrs,
2. Clinical indication for PCI
3. suitable lesion for DCB-only strategy
4. small vessel disease
5. Patient has clinical evidence of ischemic heart disease or a positive functional study
6. Patient and his or her treating physician agree that the patient will comply with all the required post-procedure follow-up.

7. One or more target lesions require treatment

Exclusion Criteria:

Patients were excluded if **ANY** of the following conditions apply:

1. Patient has active infection
2. STEMI <72 hrs, LM disease,
3. heavy calcification, thrombus-rich lesions,
4. mandatory stent requirement,
5. sirolimus allergy, pregnancy,
6. Concurrent medical condition with a life expectancy <1 yr
7. Clinically relevant contraindication to aspirin, heparin, clopidogrel bisulphate, or ticlopidine including thrombocytopenia, neutropenia, or leukopenia
8. Active peptic ulcer or upper gastrointestinal bleeding.
9. Current participation in an investigational drug or device trial that has not completed its primary endpoint follow-up period.
10. Pregnancy or woman of childbearing potential who, in the opinion of the investigator, does not take adequate measures to prevent conception

Study Design:

Comparative Arm: None (no randomization)

Centers: Multicenter – Malaysia, Myanmar

Study Duration: 12 months follow-up per patient

Introduction

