A balloon is made up of nylon material having PTFE coated stainless steel hypo tube shaft. Two radiopaque markers located underneath the balloon, fluoroscopically mark the working length of the balloon.

Available Sirolimus Drug Eluting PTCA Catheter Sizes

Diameters (mm)	Available Lengths (mm)									
1.50	06	08	10	12	15	20	25	30	35	40
2.00	06	08	10	12	15	20	25	30	35	40
2.25	06	08	10	12	15	20	25	30	35	40
2.50	06	08	10	12	15	20	25	30	35	40
2.75	06	08	10	12	15	20	25	30	35	40
3.00	06	08	10	12	15	20	25	30	35	40
3.50	06	08	10	12	15	20	25	30	35	40
4.00	06	08	10	12	15	20	25	30	35	40

Study rationale

This is a multi-center; prospective study aimed at evaluating the safety and effectiveness of the Mamba Sirolimus Drug Eluting PTCA Catheter in reducing neointimal hyperplasia and decreasing restenosis during PCI of stenotic coronary artery disease as well as intermediate-term outcomes. High Radial Strength, Excellent conformability, and Sirolimus eluting characteristics. A Drug Eluting PTCA Catheter of this type is expected to decrease restenosis following PCI and thereby improve Clinical Outcomes.

Study Procedure:

Baseline evaluation, index PCI procedure, device success, procedural success, post-angioplasty results. Follow-up at 1, 6, 12 months (clinical only).

Screening and eligibility check

Informed consent

Baseline assessment (demographics, ECG, labs, angina class)

Index DCB procedure (balloon angioplasty using Sirolimus-coated DCB)

Pre-dilatation of the target lesion with an appropriate semi-compliant or non-compliant balloon is mandatory. Only lesions with successful pre-dilatation—defined as TIMI 3 flow, no flow-limiting dissection, and $\leq 30\%$ residual stenosis—are eligible for DCB deployment."

No stent implantation unless medically necessary (bailout)

Discharge as per hospital protocol

Follow-up visits at 1, 6, and 12 months for clinical evaluation, ECG, and adverse event assessment

Follow-Up Schedule:

Timepoint	Visit Type	Assessments
Day 0	Baseline	Demographics, consent, eligibility, angina class, ECG, labs
Day 1	Procedure	DCB implantation, procedural outcomes
1 Month	Clinic visit	MACE, adverse events, ECG, medication adherence
6 Months	Clinic/Tele	MACE, TLR, adverse events, angina class
12 Months	Final visit	MACE, TLR, SAE reporting, device durability

Data Management and Monitoring:

Use of Electronic Data Capture (EDC)

On-site and remote monitoring

Centralized adjudication of endpoints by Clinical Events Committee (CEC)

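### Non-Q-wave MI is judged against normal CK with no pre-procedure reference, so an infarct already resolving at entry can meet the 30-day MACE definition without any new event

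*Protocol*

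**What the plan says.** The primary endpoint in the Protocol Summary is "MACE at 30 days". Appendix I includes both Q-wave and non-Q-wave MI in MACE.

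For non-Q-wave MI, Appendix I gives two rules:
- The main rule is "Elevation of post-procedure CK levels to > 2 times normal with elevated CK-MB in the absence of pathological Q waves".
- The fallback, which leads to the same classification, is "If no assay for CK-MB was performed, elevation of CK levels to > 2 times normal without new Q waves is also considered a non-Q-wave" (the sentence ends there with the word for infarction).

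Both measure CK as a multiple of normal. Neither mentions a pre-procedure value. The Q-wave definition next to them does look back to baseline on the ECG side, since it requires "Development of new, pathological Q waves in 2 or more contiguous leads".

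On entry, the only exclusion tied to infarction is in item 2 of the Exclusion Criteria: "STEMI <72 hrs, LM disease". The Inclusion Criteria ask for a PCI indication and evidence of ischaemic heart disease. They do not require stable disease or normal biomarkers.

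The Follow-Up Schedule lists for Day 0 "Demographics, consent, eligibility, angina class, ECG, labs" and does not say which assays the labs include. Data Management and Monitoring provides for central endpoint adjudication by a CEC. The protocol states no rule for enzymes already raised at entry.

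**The concern.** The endpoint definition overlaps with the population that the entry criteria admit. A patient with a recent infarct may arrive with CK above twice normal and CK-MB raised. If the procedure goes well and CK has not yet fallen below the threshold, a sample taken afterwards satisfies the definition although nothing new has happened.

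The study has one arm, so a false event of this kind has no counterpart in a control group to offset it. The result is a single MACE rate with a 95% confidence interval. That interval reflects sampling error and would not cover a misclassification of this sort. The reported rate would then depend partly on how many recent-infarct patients each site enrols.

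The same false event would carry into MACE at 6 and 12 months and into MACE-free survival, as an event at the start of the curve. It would also count against procedure success, which Appendix I makes conditional on no MACE during the index hospitalization.

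**Working it through.** **1. What the text admits and what it counts**

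| Step | Protocol text | Consequence |
|---|---|---|
| Entry | Exclusion Criteria, item 2: STEMI under 72 hours only | NSTEMI of any age, and STEMI at 72 hours or later, are not excluded |
| Baseline sample | Day 0: labs, no assay named | A pre-procedure CK or CK-MB is not assured |
| Event rule | Appendix I: CK above 2 × normal, CK-MB elevated (or CK alone if CK-MB was not assayed) | Can be met by an enzyme level that was already raised |
| Post-procedure sample | Day 1 and 1 Month rows name no enzyme draw | The rule operates only if a sample happens to be taken |
| Adjudication | CEC, no rule for raised baseline values | Outcome depends on how literally the CEC applies the definition |

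**2. Figures available**

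The protocol gives the sample size, 360, and a 95% CI for MACE. It gives no expected MACE rate, no share of recent-infarct patients and no precision target, so it has no figure on this point to reproduce. Everything below except 360 is an assumption.

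**3. Formula**

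Let f be the share of all subjects who become false events. It is a product:

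f = (share entering with a recent infarct) × (share of these still above threshold after the procedure) × (share sampled) × (share accepted by the CEC)

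False events are at most 360 × f. If p is the true 30-day MACE rate, the counted rate is p + (1 − p) × f.

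**4. Numbers**

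- f = 1%: 360 × 0.01 = 3.6 events.
- f = 2.5%: 360 × 0.025 = 9 events.
- f = 5%: 360 × 0.05 = 18 events.

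With an assumed p of 2% and exact (Clopper-Pearson) intervals on the rounded count:

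| f | Added events, 360 × 0.98 × f | Counted rate | Count / 360 | 95% CI |
|---|---|---|---|---|
| 0 | 0 | 2.0% | 7 | 0.8 to 4.0% |
| 1% | 3.5 | 3.0% | 11 | 1.5 to 5.4% |
| 2.5% | 8.8 | 4.5% | 16 | 2.6 to 7.1% |
| 5% | 17.6 | 6.9% | 25 | 4.5 to 10.1% |

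The added count depends little on p: at f = 5% it is 17.8 events for p = 1% and 17.1 for p = 5%. The relative effect depends heavily on p. At f = 2.5% the counted rate more than doubles when p is 2% (4.45 / 2 = 2.2), but rises by about half when p is 5% (7.38 / 5 = 1.5).

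**5. Sensitivity to sampling and adjudication**

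If 10% enter with a recent infarct and 30% of those stay above threshold, then f = 3% (360 × 0.03 = 10.8 events), provided every such patient is sampled and every case accepted. If half are sampled, f = 1.5% (5.4 events). If none is sampled, or the CEC rejects all of them, f = 0.

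**The case against.** The strongest reply is that the definition permits a false event but does not compel one. Several points support this, and most of them stand.

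- **Sampling.** No post-procedure enzyme draw is scheduled, and after an uneventful procedure none may be taken. This stands, and it is why sampling is a factor in f.
- **Wording.** The primary objective concerns MACE following treatment, and an elevation to a level can be read as a new rise. The reading is possible. But the stated threshold is a multiple of normal and no baseline sample is named, so the text does not secure it.
- **Adjudication.** The CEC could reject such cases, and its operating rules are not in this document. A reader might infer that adjudication cannot help because the CEC must apply the same definition. The protocol does not show that. It shows only that no rule is stated in the protocol, and that without a baseline value the CEC might lack the means to decide.
- **Population.** Excluding thrombus-rich lesions removes some recent-infarct patients, though not all. A reader might also take the Braunwald Class C entry in Appendix I, "Patients who develop unstable angina within the first 2 weeks after a documented acute myocardial infarction", as evidence that post-infarct patients are enrolled. It is a glossary entry, not an entry criterion, and the point does not rest on it.
- **Size.** A reader might infer a definite multiple by which MACE is inflated. Any such figure follows from an assumed base rate and an assumed f, and the protocol supports neither.

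A statistical analysis plan, which is not at hand, could state a handling rule. It could not supply a pre-procedure sample that was never required.

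**Conclusion.** The point holds in conditional form. As written, the non-Q-wave MI definition can be met by enzymes still raised from an infarct that preceded the procedure. The entry criteria admit such patients, and no named baseline sample separates the two situations. It would be too strong to say that a resolving infarct is counted as MACE. That happens only if such a patient is enrolled, CK is still above threshold afterwards, a sample is drawn and the CEC takes the wording literally.

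The size is not derivable from the protocol. About 360 × f false events are added, roughly 4 to 18 for an assumed f of 1 to 5%.

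This should be fixed, but it does not invalidate the design. The protocol plans no hypothesis test and states no performance goal, so no pass/fail decision depends on it. The error would overstate MACE, and so would not conceal harm from the device.

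**What to change.** 1. Name CK and CK-MB among the Day 0 labs, and record any recent MI on the CRF.
2. Amend the non-Q-wave MI definition in Appendix I. When pre-procedure values are normal, the current threshold applies. When they are already raised, an event also requires a new rise above the last pre-procedure value by a prespecified margin. The protocol offers no basis for a particular margin, so the sponsor and the CEC should choose and record one.
3. Where enzymes were still rising before the procedure, a margin alone would still count the presenting infarct. The CEC should judge these cases on other evidence of a new event, using earlier hospital values where they exist, since one Day 0 value cannot show the direction of change.
4. Carry the same rule into the CEC's working rules.

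The cost is two named assays in blood work already planned, a short amendment to Appendix I and a CRF item. The downside is that a small true re-infarction on a falling enzyme curve may be missed. The change should be made before enrolment goes further, because a baseline sample that was not taken cannot be recovered.

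### The MI component of MACE rests on one CK/CK-MB rule set with no time limit and no troponin route: infarcts without those assays meet neither MI type, while a CK rise without ischaemic evidence can qualify

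*Protocol*

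**What the plan says.** **Endpoints (Protocol Summary).** The primary endpoint is "MACE at 30 days". The secondary list includes "MACE at 6/12 months, TLR, TVR, SAEs, MACE-free survival". Appendix I defines MACE once for all of these: death from any cause, Q-wave or non-Q-wave MI, emergent CABG, or clinically driven TLR.

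**MI entries (Appendix I).**
- General entry: "Necrosis of the myocardium, as a result of interruption of the blood supply to the area, as in coronary thrombosis". It sets no marker, threshold, symptom, ECG or timing criterion.
- Non-Q-wave MI, main rule: "Elevation of post-procedure CK levels to > 2 times normal with elevated CK-MB in the absence of pathological Q waves".
- Non-Q-wave MI, fallback: "If no assay for CK-MB was performed, elevation of CK levels to > 2 times normal without new Q waves" also counts.
- Q-wave MI: new pathological Q waves in at least two contiguous leads, confirmed by the committee, together with post-procedure CK-MB above normal.

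Troponin appears nowhere in the protocol. No window separates peri-procedural from later MI, and no MI rule mentions symptoms.

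**Ascertainment.** The Follow-Up Schedule lists laboratory tests at baseline only. An ECG is listed at 1 month in that table, and at 1, 6 and 12 months in the Study Procedure text. Data Management and Monitoring provides for central adjudication by a Clinical Events Committee but gives it no further MI criteria.

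**The concern.** A CK/CK-MB threshold suits the hours after a procedure, when these markers may be drawn for that purpose. Here the same rule also classifies infarcts that present months later at whichever hospital admits the patient. Whether an event counts then depends partly on which assay that hospital ran, and the trial spans two countries.

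The errors run both ways. Genuine infarcts without the required assay are left out. Total CK alone, without ischaemic evidence, can be let in. The design is single-arm and the main result is a MACE proportion with its 95% CI, so there is no control arm in which such misclassification could cancel.

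**Working it through.** The protocol states no MI or MACE rate behind this definition and no derivation of the 360, so there is no figure to reproduce. The check has two parts.

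**1. Apply the rules as written to five patterns.**

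| Pattern | Q-wave rule | Non-Q-wave main rule | Fallback | Counts as MI? |
|---|---|---|---|---|
| A. Later infarct, CK > 2 times normal, CK-MB raised, no Q waves | no | yes | not applicable | Yes |
| B. Symptoms, ECG change without Q waves, raised troponin; no CK or CK-MB assay | no | no | no | **No** |
| C. New Q waves, CK > 2 times normal, CK-MB not assayed | no (no CK-MB) | no (Q waves present) | no (new Q waves) | **No** |
| D. CK > 2 times normal, CK-MB not assayed, no new Q waves, no symptoms (e.g. muscle injury) | no | no | yes | **Yes** |
| E. As D, but CK-MB assayed and normal | no | no | not applicable | No |

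- A shows that the wording has no end date, so late infarcts are not excluded as a class.
- B is the troponin gap.
- C against D is an inversion: with the same CK and no CK-MB assay, the patient with new Q waves is not counted and the patient without them is.
- D against E shows that the same clinical event changes class according to whether CK-MB was ordered.
- New Q waves first seen on a scheduled follow-up ECG have no scheduled CK-MB beside them. At 1 month this bears on the primary endpoint.

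**2. Scale.**

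Input from the protocol: n = 360. One patient moves a proportion by 1/360 = 0.28 points.

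Assumptions, not in the protocol: spontaneous MI by 12 months in a proportion r of patients (1-3%, centre 2%); a share s of these documented on troponin only (25-75%, centre 50%).

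Infarcts not countable = 360 × r × s. In points this is 100 × r × s.
- Low: 360 × 0.01 × 0.25 = 0.9 patients; 0.9/360 = 0.25 points
- Centre: 360 × 0.02 × 0.50 = 3.6 patients; 3.6/360 = 1.0 point
- High: 360 × 0.03 × 0.75 = 8.1 patients; 8.1/360 = 2.25 points

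These are ceilings for MACE. If a fraction v of such patients also die or have emergent CABG or clinically driven TLR by 12 months, they are MACE cases anyway, and the loss is 100 × r × s × (1 − v).

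Illustration with an assumed true count of 18 events in 360, exact (Clopper-Pearson) 95% CI:

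| Scenario | Events | MACE | 95% CI |
|---|---|---|---|
| Correct classification | 18 | 5.0% | 3.0-7.8 |
| 4 infarcts not counted | 14 | 3.9% | 2.1-6.4 |
| 7 infarcts not counted | 11 | 3.1% | 1.5-5.4 |
| 4 CK-only rises added | 22 | 6.1% | 3.9-9.1 |
| 7 CK-only rises added | 25 | 6.9% | 4.5-10.1 |

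For comparison, the normal-approximation half-width at 5% is 1.96 × √(0.05 × 0.95/360) = 2.25 points.

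**The case against.** **The general MI entry and the committee cover the gaps.** The general entry is the parent concept, and a CK rise from skeletal muscle is not myocardial necrosis. Endpoints are adjudicated centrally, and a charter may exist that was not available here. Part of this stands: adjudication may reduce both errors, so neither is certain in a given patient. But the general entry contains nothing measurable, MACE refers to the two typed entries, and the protocol gives the committee no other MI criteria. A committee that follows the text has to reject patterns B and C and may accept D.

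**Only descriptive estimates are affected.** This is correct. The protocol plans no formal hypothesis test, so no pass/fail decision turns on the definition. The MACE estimate and its interval are nevertheless the trial's main result.

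**Stronger readings that the document does not support.** A reader might infer:
- that infarcts after discharge cannot be counted at all. They can when CK and CK-MB are measured and sufficiently raised, because the post-procedure period has no end date.
- that any non-cardiac CK rise counts. The evident route is the fallback, which opens only when CK-MB was not assayed.
- that 12-month MACE is understated by about 1 point. That figure is a ceiling under assumed inputs. It ignores overlap with death, CABG and TLR, and the opposing over-count.
- that target vessel failure is also affected as an endpoint. It is defined in Appendix I but is not among the listed endpoints.

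**Conclusion.** The point holds in this limited form. The rules in Appendix I, applied as written, exclude infarcts documented without the required CK/CK-MB, exclude new Q waves without a CK-MB assay even when CK exceeds the threshold, and admit total CK alone where CK-MB was not assayed. This is a stated rule that misclassifies, not a detail left for a later document. It affects MACE at 30 days, 6 months and 12 months, and MACE-free survival.

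The net direction of bias cannot be determined from the document. The 12-month under-count is at most 0.25-2.25 points under the assumed rates. The over-count is not estimated, because the protocol gives no basis for how often CK would be drawn without CK-MB. The definition should be corrected, though the likely effect is a modest shift in a descriptive estimate.

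**What to change.** Amend the MI entries in Appendix I and align the committee charter:

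1. Limit the CK/CK-MB rule to a stated peri-procedural window.
2. After that window, define spontaneous MI as troponin or CK-MB above the upper limit, plus at least one of ischaemic symptoms, new ischaemic ECG change or new Q waves, or imaging or angiographic evidence.
3. Do not let total CK alone make an MI at any time, inside or outside the window, without supporting evidence of ischaemia.
4. State how new Q waves without a CK-MB result are classified.

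The cost is wording in Appendix I and the charter. No visits are added, and the markers are ones that hospitals already draw for suspected infarction. The downside for the sponsor is that reported MI and MACE may be slightly less favourable. The change does not add scheduled sampling, so detection of silent peri-procedural infarction would still depend on local practice.

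### Procedure success has no stated status for bailout stenting, so a lesion rescued with a stent can be counted as a success, and no listed endpoint reports how often this happens

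*Protocol*

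**What the plan says.** All references are to the protocol.

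- **Inclusion/Exclusion criteria.** The inclusion criteria ask for a "suitable lesion for DCB-only strategy", and a "mandatory stent requirement" is an exclusion.
- **Study Procedure.** Pre-dilatation is mandatory, and only lesions that meet its three criteria (flow grade, dissection, residual stenosis of at most 30%) "are eligible for DCB deployment". On stents the section says "No stent implantation unless medically necessary (bailout"). It attaches no consequence for any endpoint.
- **Appendix I, procedure success rate.** "Percentage of patients with angiographic success and without the occurrence of MACE during the index hospitalization".
- **Appendix I, MACE.** "Composite of Death (Both Cardiac & Non-Cardiac Death), MI (Q-wave and Non-Q-wave), (emergent"), continuing with "CABG or clinically driven Target Lesion Revascularization (TLR").
- **Appendix I, TLR.** "Any repeat treatment of the stented segment including 5 mm proximal and 5 mm distal from the edge of the stent".
- **Endpoints.** Device success and procedural success are separate secondary endpoints. The bailout rate is not listed. Neither device success nor angiographic success is defined in the protocol.
- **Statistical Analysis Plan (SAP) section.** ITT and PP populations are named without definition. The analysis is descriptive, with a 95% CI for MACE and no hypothesis test.

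**The concern.** A bailout stent departs from the strategy for which the lesion was selected. A success endpoint for a drug-coated balloon should say whether such a case is a success or a failure, and this one does not. Success rests on an undefined term plus the absence of in-hospital MACE, and a stent placed during the index procedure does not appear among the MACE components.

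The study is single-arm and descriptive and is meant to support a clinical evaluation report, so the reported success rate is itself the result. If rescued lesions sit among the successes and the bailout rate is not reported beside it, a reader cannot tell how often the balloon alone was enough.

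**Working it through.** **1. Is there a plan figure to reproduce?** No. The protocol gives 360 subjects without a derivation, and it gives no bailout rate and no expected success rate. The point rests on the definitions; the arithmetic only shows scale.

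**2. One patient traced through the definitions.** Take a lesion that passes pre-dilatation, is treated with the DCB, then receives a bailout stent. The patient leaves hospital with an open vessel and no further event.

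- Death, MI, CABG: none occurred.
- TLR: this requires repeat treatment, so a stent placed within the index procedure does not qualify.
- In-hospital MACE: therefore absent.
- Angiographic success: undefined. The only lesion-result criteria in the protocol are the three pre-dilatation ones, and a stented lesion could meet all of them.

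Nothing written stops this patient being scored a success. Nothing written says that the patient must be.

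**3. Effect on the success rate.** Let *b* be the bailout share and *q* the fraction of bailout patients who otherwise meet the definition. Counting bailout as failure lowers the rate by *b × q*, which is at most *b*. Inputs: n = 360 (protocol); success with bailout counted as success 97%, i.e. 360 × 0.97 ≈ 349 (assumed); *b* from 2% to 15% (assumed); *q* = 1 (worst case). Intervals are exact (Clopper-Pearson). With bailout counted as success, 349/360 has a 95% CI of 94.6% to 98.5%.

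| b | Bailout patients | Success if bailout is failure | 95% CI |
|---|---|---|---|
| 2% | 7 | 342/360 = 95.0% | 92.2% to 97.0% |
| 5% | 18 | 331/360 = 91.9% | 88.6% to 94.5% |
| 10% | 36 | 313/360 = 86.9% | 83.0% to 90.2% |
| 15% | 54 | 295/360 = 81.9% | 77.6% to 85.8% |

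From *b* = 5% upward the interval no longer overlaps 94.6% to 98.5%. These are two scorings of the same patients, so this shows only that the choice of rule outweighs sampling error.

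**4. Would a PP population that removes bailout patients show the failures?** At *b* = 5% and *q* = 1, removing 18 patients from numerator and denominator gives (349 − 18)/(360 − 18) = 331/342 = 96.8%. That is almost the unadjusted 96.9% (349/360). Exclusion hides these cases as effectively as counting them as successes.

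**5. Effect on later outcomes.** Pooled TLR = (1 − b) × p_DCB + b × p_bailout, so the shift from the DCB-only rate is b × (p_bailout − p_DCB). Assume 12-month TLR of 5% with the DCB alone and 2% to 10% after bailout:

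- b = 5%: 0.05 × (2 − 5) = −0.15 points to 0.05 × (10 − 5) = +0.25 points
- b = 10%: −0.30 to +0.50 points
- b = 15%: −0.45 to +0.75 points

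The approximate 95% CI half-width is 1.96 × √(0.05 × 0.95/360) = 2.25 points. In this range pooling is a minor matter; the weight lies on the success endpoint.

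**The case against.** The strongest reply is that this is silence, not a stated rule. Angiographic success may be meant to exclude stented lesions, and device success, listed separately, may be where bailout counts as failure. Definitions of ITT and PP and table layouts are commonly left to a statistical analysis plan, which is not at hand. Bailout is captured in any case, since the Technician's Work Sheet in the CRF records procedure details. The bailout rates above are assumed, and the fall in success simply returns them. Bailout patients with a qualifying enzyme rise already fail through non-Q-wave MI, and the pre-dilatation requirement may keep bailout uncommon.

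Much of this stands. That a rescued lesion *is* a success cannot be claimed, only that it *can* be. The shift is an upper bound, and the undefined populations are not a finding here. What does not fall away is that the protocol itself sets the procedure success definition and leaves bailout out of it. Recording bailout in the CRF is not the same as reporting it. A population label does not settle it either: under ITT the case can remain a success, and a PP exclusion would drop it. Nor are separate bailout rows secured, because the protocol mentions exploratory subgroup analysis and then says that none is planned.

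A reader might infer that the trial cannot answer a DCB-only question, or that outcomes after a bailout stent are credited to the balloon. The documents support neither. DCB-only appears as a lesion-suitability criterion, while the primary objective is MACE at 30 days after treatment with the device. Keeping bailout patients in an ITT analysis is a legitimate evaluation of a balloon strategy with provisional stenting, and no section says how later events are attributed.

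**Conclusion.** The point holds as a gap in the definition of a secondary endpoint that is cheap to close. As written, a lesion selected for DCB-only treatment but rescued with a stent can be counted as a procedure success, and no listed endpoint gives the frequency. The possible overstatement of DCB-only success is at most the bailout share: 2 to 15 points over the assumed range, or about 5 points (97% to 91.9%) at 5% bailout. This rests on assumed bailout and success rates and on every bailout patient otherwise meeting the definition. The stated primary objective is not undermined, and the effect of pooling on 12-month TLR is small against its CI under the rates assumed.

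**What to change.** - Define angiographic success and device success in Appendix I, and state that bailout stenting of the target lesion is a failure of device success (DCB-only success).
- Give procedure success the same status, or report it both with and without bailout cases counted as successes.
- Report the bailout rate with its 95% CI.
- Keep all-patient (ITT) MACE and TLR as the main results, and add descriptive rows for patients treated with the DCB alone and for bailout-stented patients. The TLR wording needs correcting at the same time: it is tied to a stented segment and, read literally, does not fit a lesion treated by balloon alone.

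The cost is protocol wording, a few table rows and a less favourable headline success rate. The change concerns endpoint definitions and reporting only; no view is taken on when a bailout stent should be used.
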